## Research Design and Methods

---

Describe in detail the methods and procedures that will be used to accomplish the objectives and specific aims of the project. Discuss the alternative methods that are available and justify the use of the method proposed in the study. Justify the scientific validity of the methodological approach (biomedical, social, or environmental) as an investigation tool to achieve the specific aims. Discuss the limitations and difficulties of the proposed procedures and sufficiently justify the use of them. Discuss the ethical issues related to biomedical and social research for employing special procedures, such as invasive procedures in sick children, use of isotopes or any other hazardous materials, or social questionnaires relating to individual privacy. Point out safety procedures to be observed for protection of individuals during any situations or materials that may be injurious to human health. The methodology section should be sufficiently descriptive to allow the reviewers to make valid and unambiguous assessment of the project. **(DO NOT EXCEED TEN PAGES, USE CONTINUATION SHEETS).**

---

This study has two parts to address its two objectives, which complement each other, and will be done, in sequence to test our hypothesis.

1. **First part:** To determine prevalence of *H. pylori* infection, low gastric acid secretion and IDA in Bangladeshi women in the reproductive age living in a peri-urban community of Dhaka City.
2. **Second part:** To conduct a randomized, double-blind, placebo-controlled field trial in the same population to determine if *H. pylori* infection is causally linked to iron deficiency anemia in this population.

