## 2. Part 2: Testing of the second objective

### Randomized, double-blind, placebo-controlled, community trial

#### 2.1 Methods

To determine if there is a causal relationship of IDA with Hp infection, or if Hp infection has any relationship with IDA, an intervention study will be conducted on 100 Hp-infected women with hypochlorhydria and IDA. They will be randomized in equal numbers to receive either of the following four interventions:

- (i) Anti Hp therapy: A combination of 500mg clarithromycin twice daily + 500mg amoxicillin twice daily + 40 mg omeprazole once daily for 14 days
- (ii) Anti Hp therapy plus iron: The above + ferrous fumarate containing 60-mg elemental iron each day for 60 days
- (iii) Iron alone: Ferrous fumarate containing 60-mg elemental iron each day for 60 days
- (iv) Placebo: Starch powder

**Fifth group:** There will be a fifth group of 25 women with Hp infection but without hypochlorhydria. This group is required to observe the influence of hypochlorhydria *per se* on IDA. This group will also be treated with Anti-Hp therapy plus iron.

The therapies will be provided in gelatin capsules and will be fed daily in morning and at the evening. The women in the placebo group will receive same amount of starch powder in identical capsules for 60 days. To keep the study blind, all therapies will be kept in identical container and will be fed by a health worker who will remain unaware of the nature of the study and the contents inside the bottles.

The women will be followed for six months after the end of intervention. Hb, SF, and sTfR will be determined at the end of intervention and also, 3 and 6 months after the intervention. Urea breath test will also be performed at the same time. EIT will be repeated 6 months after intervention. The women in the placebo groups will be given anti-Hp therapy plus iron as indicated above at the end of study period of 6 months. Similarly the group (iii) women will also provided anti-Hp therapy at the end of the study. The dose of iron conforms to that used in Bangladesh ( Kolsteren et al 1999).

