### 2.6.1 Outcome Measures

- Prevalence of Hp infection and hypochlorhydria before and after intervention
- Prevalence of IDA in each group before and after the intervention
- Rise of serum Hb and SF, transferrin saturation, and reduction in sTfR before and after intervention
- Change of gastric acid output before and after intervention.

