## Data Analysis

Describe plans for data analysis. Indicate whether data will be analyzed by the investigators themselves or by other professionals. Specify what statistical software packages will be used and if the study is blinded, when the code will be opened. For clinical trials, indicate if interim data analysis will be required to monitor further progress of the study. **(TYPE WITHIN THE PROVIDED SPACE).**

Principal Investigator (Last, first, middle): [name]

Data will be entered onto personal computer (PC) and analyzed by the investigators themselves using the Windows version of the Statistical Package for Social Science (SPSS).

Chi square test will be used for comparison of the proportions of IDA in Hp-infected women with normal acid secretion (>300 AUC) versus women with low acid secretion (AUC <300).

Clinical characteristic such as age and weight, and laboratory characteristics such as Hb, SF, and sTfR concentration will be compared among the groups by one way analysis of variance (ANOVA). When significant F ratio ( $p < 0.05$ ) is obtained, means will be compared by student's t-test using multiple comparison procedure. Outcome variables e.g. change in the Hb, SF and sTfR, and gastric acid output before and after intervention in each group will be compared using paired t-test. Data with skewed distribution will be normalized using log transformation, and the t-test will be applied on transformed data. Chi-square ( $X^2$ ) test will be applied for comparison of binary variables e.g. the incidence of Hp infection with hypochlorhydria and IDA before and after therapy, and also for comparison between groups. The Odd's Ratio (OR) and Confidence Interval (CI) will be calculated. Multivariate analysis (logistic regression and multiple regression) will be done for adjustment of confounding variables such as age, socioeconomic status, and nutritional status .

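### The H. pylori protocol tests change in Hb, ferritin, transferrin receptor and gastric acid output only within each arm and specifies no clear between-arm comparison of them

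*Protocol*

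**What the plan says.** This concerns only the H. pylori protocol, one of two unrelated protocols in the file. Its Research Design and Methods section gives this aim for the randomised component: "To conduct a randomized, double-blind, placebo-controlled field trial in the same population to determine if *H. pylori* infection is causally linked to iron deficiency anemia". Section 2.1 takes 100 infected women with hypochlorhydria and iron deficiency anaemia (IDA) and says "They will be randomized in equal numbers to receive either of the following four interventions". A fifth group of 25 women without hypochlorhydria is added and is not randomised.

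The Data Analysis section then assigns methods:

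- **Continuous outcomes:** "change in the Hb, SF and sTfR, and gastric acid output before and after intervention in each group will be compared using paired t-test".
- **Binary outcomes:** chi-square for "the incidence of Hp infection with hypochlorhydria and IDA before and after therapy, and also for comparison between groups", with odds ratio and confidence interval.
- **Characteristics:** alongside age and weight, "laboratory characteristics such as Hb, SF, and sTfR concentration will be compared among the groups by one way analysis of variance (ANOVA", followed by t-tests with a multiple comparison procedure if the F ratio is significant.
- **Regression:** logistic and multiple regression, to adjust for confounders such as age, socioeconomic status and nutritional status.

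Section 2.6.1 frames the outcomes in the same before-after way, for example "Prevalence of IDA in each group before and after the intervention".

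**The concern.** A paired t-test within an arm asks whether that arm moved. It does not ask whether the arm moved more than its randomised comparator, which is the question a placebo group exists to answer.

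Two features of this trial make that matter.

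- **Selection on the outcomes.** Women qualify by having Hb below 12 g/dL plus two of three abnormal iron measurements (section 1.1.4.2), and by an AUC below 300 (section 1.1.2). These are the quantities tested afterwards, so regression to the mean pushes every arm towards normal, placebo included.
- **Expected response in both arms of the sized contrast.** Section 2.3 assumes anaemia is corrected in 60% on iron alone and 95% on anti-Hp therapy plus iron. Hb should therefore rise in both arms, and two significant paired tests would say nothing about the difference between them.

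The before-after chi-square has a related fault. It treats two measurements on the same women as independent samples, and IDA before treatment is 100% by entry criterion.

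At stake is that a before-after rise is reported as an effect of treatment. Acid output is most exposed: it is the proposed mechanism, and it has no named between-arm test.

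**Working it through.** **1. The plan's own figure.** Section 2.3 uses n = 2P(1-P)(Zα/2 + Zβ)²/D², with P = 0.775, D = 0.35, Zα/2 = 1.96 and Zβ = 0.86:

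n = 2 × 0.775 × 0.225 × 2.82² / 0.35² = 22.64, rounded up to 23.

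This reproduces. It sizes a between-arm comparison of a binary outcome, with approximate power 0.83 at 23 per arm. The checks below use 23 per arm.

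**2. Is a between-arm test of the continuous outcomes specified elsewhere in Data Analysis?**

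- *ANOVA:* covers Hb, SF and sTfR concentration. No time point is given, they are listed with age and weight, and the text turns to outcome variables only afterwards. It reads as a baseline comparison. Neither change nor acid output is named.
- *Multiple regression:* no outcome, treatment term or baseline value is stated.
- *Between-group chi-square:* binary variables only.

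So no clear between-arm comparison is fixed for Hb, SF or sTfR, and none is named for acid output.

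**3. Paired t-test with no treatment effect and a drift common to all arms.** The documents give no drift, so d, in SD units of change, is assumed. The statistic is non-central t with 22 df and non-centrality d√23. With p the chance that one arm is significant, two identical arms disagree with probability 2p(1-p).

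| d | p (one arm significant) | 2p(1-p) |
|---|---|---|
| 0 | 0.05 | 0.10 |
| 0.2 | 0.15 | 0.26 |
| 0.4 | 0.45 | 0.50 |
| 0.6 | 0.79 | 0.34 |
| 0.8 | 0.96 | 0.08 |

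**4. Regression to the mean from Hb selection alone.** From the documents: Hb at entry from 8 (section 2.4) to below 12 g/dL. Assumed: population mean 11-12 g/dL, SD 1.2, test-retest correlation r of 0.8-0.9, and the screening value used as the before value. Simulated, with no treatment effect:

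| Mean, r | Mean change (g/dL) | Paired t rejects | Between-arm t on change rejects |
|---|---|---|---|
| 11.0, 0.8 | 0.081 | 7.7% | 4.7% |
| 11.5, 0.9 | 0.066 | 8.8% | 5.0% |
| 11.5, 0.8 | 0.131 | 13.0% | 5.0% |
| 12.0, 0.8 | 0.190 | 21.9% | 4.9% |

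**5. Before-after chi-square on IDA.** All 23 women have IDA at entry. If 4 resolve without treatment, the table is 23/0 v 19/4:

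χ² = 46 × (23×4 - 0×19)² / (23×23×42×4) = 4.38, p = 0.036.

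Exact McNemar on the same four changes gives 2 × 0.5⁴ = 0.125. The small p therefore owes much to a large-sample approximation in a sparse table (two expected counts of 2). It is not evidence that ignoring the pairing alone creates significance: uncorrected McNemar is 4²/4 = 4.0, close to 4.38. No before-after test, paired or not, separates treatment from drift.

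**The case against.** The strongest reply is that the paired t-tests are not the whole plan. The chi-square is also planned "and also for comparison between groups", with odds ratio and confidence interval, and correction of anaemia is the outcome on which the trial was sized. That stands. A reader might infer from the paired t-tests that the trial cannot answer its causal question or throws away its randomisation; the documents do not support that.

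A second reply is that nothing confines the ANOVA to baseline, and an ANOVA at follow-up would be a between-arm test. This stands in part. For Hb, SF and sTfR the fault is an unstated time point and an unfavourable context rather than a proven absence. The reading does not help acid output, which the ANOVA sentence does not name.

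Third, the protocol nowhere says that significance in one arm and not in another will be taken as a treatment difference. That is true. The disagreement rates in the working show what such a reading would cost; they do not describe a rule in the plan.

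Fourth, drift, SD and retest correlation are assumed, and the disagreement probability peaks at 0.50 by construction. That also stands.

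Finally, model details belong in an analysis plan that is not shown. But the protocol does not leave the test open: it names one, and it is within-arm.

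**Conclusion.** The point holds for the continuous outcomes. The protocol fixes a within-arm test for change in Hb, SF, sTfR and acid output and specifies no clear between-arm comparison of them. Such a test estimates no treatment effect and can be significant on placebo.

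The size is illustrative. Under the assumptions shown, 8-22% of untreated arms are significant from Hb selection alone. A common drift of 0.2-0.8 SD raises this to 15-96%. A between-arm test of change stays at about 5% in the Hb-selection simulations. If Hb were measured again after screening and that value used as baseline, the selection effect would be smaller. Only the direction is certain.

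The before-after chi-square on IDA is unsuitable as a test of treatment, because the data are paired and the starting proportion is fixed at 100%. The between-group chi-square for correction of anaemia is unaffected.

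**What to change.** - **Hb, SF, sTfR and acid output:** replace the paired t-tests as the outcome analysis with ANCOVA across the four randomised arms, on the follow-up value at a named time point with its baseline as covariate, on the log scale where skewed.
- **Contrasts:** name (ii) v (iii), anti-Hp plus iron against iron alone, which was the one sized; and (i) v (iv), anti-Hp against placebo. Use the same contrasts in the between-group comparison of correction of anaemia that is already planned.
- **ANOVA:** state its time point. If it is meant as a baseline description, say so.
- **Before-after change:** keep it as description by arm. If binary before-after data are tested at all, use a paired method such as McNemar, and do not present the result as a treatment effect.
- **Fifth group:** report it separately, since it is not randomised.

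The cost is a change of analysis wording. The data, visits and software stay the same.

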### 1.1.4.2. Definition of iron deficiency anaemia

Iron deficiency anaemia will be defined as: haemoglobin value below the WHO cut-off for women (12 g/dL) (Dallman et al 1995) plus two out of three abnormal Fe status measurements; plasma ferritin values <12 g/L, plasma circulating transferrin receptor values >8.5 mg/L (Cook et al 1993) and transferrin saturation values <15%.

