### 2.3 Sample size

The sample size is determined with the assumptions that anaemia will be corrected in 95% women with Anti-Hp therapy plus iron-therapy, while iron therapy alone will correct anaemia in 60% of the women. Thus, the worthwhile difference (D) in correction of anemia will be:

$$D = 95 - 60 = 35\%$$

At 5% level of significance (type I error of 5%) with 80% power (type II error of 20%), and to detect a 35% difference in the outcome (correction of anaemia), the sample size has been estimated as follows:

$$n = 2 P(1-P) * (Z_{\alpha/2} + Z_{\beta})^2 / D^2$$

Where:  $P = (P_1 + P_2) / 2 = (95 + 60) / 2 = 77.5 \%$   
(  $P_1$  is 95% and  $P_2$  is 60% )

$$\begin{aligned} n &= 2 * 0.775 (1-0.775) * (1.96 + 0.86)^2 / (0.35)^2 \\ &= 1.55 * 0.225 * (2.82)^2 / 0.1225 \\ &= 0.34875 * 7.95 / 0.1225 \\ &= 22.6 \\ &\cong 23 \text{ subjects in each of the five groups} \end{aligned}$$

Based on previous study in the same community, we anticipate a drop out rate of approximately 10%. Therefore, the number of women to be enrolled is 25 in each group i.e.  $25 * 5 = 125$  women in total in 5 groups.

The reported prevalence of Hp infection is 80%. We estimate 60 % of infected population will be hypochlorhydric. of whom 70% will have IDA. We need to screen 298 ( $100 / 0.8 * 0.6 * 0.7$ ) women to identify 100 infected women (for four groups) with hypochlorhydria and iron deficiency anemia. As 160 women will be enrolled under the first part of the study we will require 138 ( $298 - 160 = 138$ ) additional women to be screened under the second part of the study.

We need a fifth group of 25 women with Hp infection but without hypochlorhydria. They will be selected from among these 260 women.

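### H. pylori protocol, Part 2: the only binary variable named for comparing treatment groups contains Hp infection itself and does not match the anaemia outcome on which the trial is sized

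*Protocol*

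**What the plan says.** The file holds two protocols. This point concerns only the second, on Hp infection, hypochlorhydria and IDA, and within it Part 2, the randomised trial. The aim of Part 2 is to find out whether Hp infection is causally linked to IDA.

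- **Population (2.1 Methods):** "an intervention study will be conducted on 100 Hp-infected women with hypochlorhydria and IDA". These women are randomised equally to (i) anti-Hp therapy, (ii) anti-Hp therapy plus iron, (iii) iron alone or (iv) placebo. A fifth group of 25, outside this randomisation, has Hp infection without hypochlorhydria.
- **Sample size (2.3):** it assumes that "anaemia will be corrected in 95% women with Anti-Hp therapy plus iron-therapy" and that "iron therapy alone will correct anaemia in 60% of the women". The trial is sized "to detect a 35% difference in the outcome (correction of anaemia").
- **Outcome list (2.6.1):** "Prevalence of IDA in each group before and after the intervention". Hp infection and hypochlorhydria form a separate item. Correction of anaemia is not listed under that name.
- **Definition of IDA (1.1.4.2):** haemoglobin below 12 g/dL "plus two out of three abnormal Fe status measurements".
- **Data Analysis:** the chi-square test is to be used for binary variables, with one example: "the incidence of Hp infection with hypochlorhydria and IDA before and after therapy, and also for comparison between groups". The words just before it mark it as an example. The section's other chi-square compares IDA between women with normal and low acid secretion, not between treatments.

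No binary outcome is designated as the one on which the trial is to be judged.

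**The concern.** Three sections point to three different binary variables. The one that Data Analysis links to treatment comparisons is unsuited to the aim. If it is a joint state (Hp infection and hypochlorhydria and IDA all present), anti-Hp therapy acts directly on one of its parts. A woman leaves the state by clearing Hp, with her haemoglobin, iron markers and acid output unchanged. A lower frequency of the joint state in a treated group would then show that the antibiotics cleared the infection. The trial asks something else: whether clearing the infection corrects the anaemia.

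The joint state is also fixed by selection at entry. Groups (i) to (iv) are recruited for having it and the fifth group for lacking one part of it. The before/after comparison therefore starts from a ceiling, and a comparison with the fifth group carries no information.

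**Working it through.** **Step 1. The plan's own sample size.** Section 2.3 uses n = 2P(1-P)(Zα/2 + Zβ)²/D², with P = (0.95 + 0.60)/2 = 0.775, D = 0.35, Zα/2 = 1.96 and Zβ = 0.86:

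n = 2 × 0.775 × 0.225 × 2.82² / 0.1225 = 22.6, rounded to 23.

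This reproduces the stated figure. It was derived for correction of anaemia, with no reference to Hp status.

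**Step 2. Joint state at entry.** Groups (i) to (iv): 100%, because it is their entry criterion. Fifth group: 0%, because these women do not have hypochlorhydria.

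**Step 3. Joint state at follow-up if anti-Hp therapy has no effect on anaemia or acid.** Let c be the proportion in whom anaemia is corrected (the same in both groups, and here also counted as no longer IDA), h the proportion in whom hypochlorhydria persists, and e the eradication rate. Assume that these are independent and that no woman in the comparator group clears Hp. Then:

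- comparator group: (1 - c) × h
- anti-Hp group: (1 - c) × h × (1 - e)

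From the protocol: c = 0.60 on iron alone, here applied to both iron groups. Assumed, because the protocol gives no figure: e from 0.5 to 0.9, h from 0.7 to 1.0, and c from 0 to 0.1 without iron.

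Example for (ii) against (iii), h = 1, e = 0.9: 0.40 × 1 = 40% on iron alone, and 0.40 × 1 × 0.1 = 4% on anti-Hp plus iron.

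**Step 4. How often the chi-square is significant.** Exact enumeration of the uncorrected chi-square, 23 per group, two-sided 5%, with no effect on anaemia:

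| Comparison | h | e = 0.5 | e = 0.7 | e = 0.8 | e = 0.9 |
|---|---|---|---|---|---|
| (ii) v (iii), c = 0.6 | 1.0 | 32% | 61% | 77% | 91% |
| (ii) v (iii), c = 0.6 | 0.7 | 22% | 43% | 57% | 74% |
| (i) v placebo, c = 0 | 1.0 | 100% | 100% | 100% | 100% |
| (i) v placebo, c = 0 | 0.7 | 69% | 94% | 99% | 99.9% |
| (i) v placebo, c = 0.1 | 1.0 | 94% | 99.8% | 100% | 100% |
| (i) v placebo, c = 0.1 | 0.7 | 60% | 89% | 97% | 99.6% |

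The same test on IDA alone is significant in 5.1% of trials at c = 0.6, 4.5% at c = 0.1 and 0% at c = 0.

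**The case against.** The strongest reply is that the phrase is only an example. The sentence covers binary variables in general, and IDA prevalence is a listed binary outcome, so the same chi-square could be applied to IDA alone. This stands: the protocol does not confine itself to the joint state. But it is the only example given for treatment comparisons, and nothing gives another variable priority.

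A second reply is that the phrase may be shorthand for the first two items of 2.6.1, Hp infection with hypochlorhydria on one side and IDA on the other. That cannot be excluded. The joint reading is the more natural one, since the Part 1 sample size (1.1.5) estimates the prevalence of the same three conditions combined. If shorthand was meant, the sentence still needs correcting.

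Third, the rates in the illustration come from outside the protocol, and the Background expects frequent treatment failure and reinfection. This also stands, and is why the range goes down to 50% eradication.

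A reader might infer more than the documents support:

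- *That anti-Hp therapy succeeds by definition, or that the trial would necessarily declare causality.* The joint state does fall mechanically, but for (ii) against (iii) significance ranges from 22% to 91%. Haemoglobin, ferritin, transferrin receptor, IDA prevalence and acid output are also assessed, and nothing makes the joint variable decisive.
- *That one endpoint has been given three definitions.* No binary endpoint is designated. The sections use different variables.
- *That using IDA in place of anaemia costs power.* The two are different events under 1.1.4.2, because iron markers can normalise while haemoglobin stays below 12 g/dL. But 2.3 itself moves between anaemia and IDA, so its 95% and 60% may already refer to IDA. Any loss of power would rest on assumed shifts in the markers.

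**Conclusion.** The concern holds as an inconsistency with a specific consequence. Sections 2.3, 2.6.1 and Data Analysis do not name the same binary outcome, and the one named for treatment comparisons, read naturally, includes the infection that the treatment is meant to remove. A difference in that variable cannot support the claim that Hp causes IDA.

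If it were used, and anti-Hp therapy did nothing for anaemia, a significant result would appear in about 22-91% of trials for (ii) against (iii), the comparison on which the trial is sized, and in about 60-100% for (i) against placebo. Without Hp status in the endpoint the figure is about 5% or less. These figures depend on the assumed eradication and persistence rates and on independence between them. The direction does not: in this no-effect setting, any eradication lowers the joint state.

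**What to change.** In Data Analysis, replace the joint variable for between-group efficacy comparisons with one binary endpoint that leaves out Hp status. Two choices fit the protocol: correction of anaemia, as sized in 2.3, or resolution of IDA, as defined in 1.1.4.2. Use the same term in 2.3, 2.6.1 and Data Analysis. If resolution of IDA is chosen, state in 2.3 that the 95% and 60% refer to it. Test Hp clearance and acid status separately from IDA, which 2.6.1 already lists as its own item.

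The schedule for acid status should be reconciled at the same time. Section 2.1 repeats the acid measurement only 6 months after intervention, while the Project Summary also lists the end of intervention and 3 months. The time point of the endpoint and the order of the comparisons can be left to the analysis plan.

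The cost is wording in three sections. No new data are needed and the 23 per group stays. The one thing given up is a joint outcome that would tend to look more favourable.
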